**<each group>:**

RSV-Ld = Low dose ChAd155-RSV vaccine (5 x 10^9 vp)  
 RSV-Md = Middle dose ChAd155-RSV vaccine (1.5 x 10^10 vp)  
 RSV-Hd = High dose ChAd155-RSV vaccine (5 x 10^10 vp)  
 Placebo-Ld = Non-active control (0.5 ml)  
 Placebo-Md = Non-active control (0.15 ml)  
 Placebo-Hd = Non-active control (0.5 ml)  
 N = number of subjects with at least one available result for the specified laboratory parameter and follow-up period  
 n/% = number/percentage of subjects reporting at least once the laboratory event when the maximum grading over the follow-up period is considered  
 SCR=Screening

**Template 26 Descriptive statistics table on eosinophils, basophils, and monocytes counts for subjects <Exposed Set>**

		Each Group N=			
		95% CI			
Parameters	Timing	Parameter	Value	LL	UL
Eosinophils	SCR	n			
		Mean			
		95% CI			
		Q1			
		Median			
		Q3			
		Min/Max			
	PI(D2)				
	PI (D8)				
	PI (D31)				
	PII (D32)				
PII (D38)					
Basophils					
Monocytes					

RSV-Ld = Low dose ChAd155-RSV vaccine ( $5 \times 10^9$  vp)  
 RSV-Md = Middle dose ChAd155-RSV vaccine ( $1.5 \times 10^{10}$  vp)  
 RSV-Hd = High dose ChAd155-RSV vaccine ( $5 \times 10^{10}$  vp)  
 Placebo-Ld = Non-active control (0.5 ml)  
 Placebo-Md = Non-active control (0.15 ml)  
 Placebo-Hd = Non-active control (0.5 ml)  
 N = number of subjects in each group  
 n= Number of subjects with result available  
 SD=Standard Deviation  
 Q1, Q2 and Q3 = 1st, 2nd (median) and 3rd quantiles  
 Min/Max = Minimum/Maximum  
 95% CI = exact 95% confidence interval, LL = Lower Limit, UL = Upper Limit

**Figure 2** Individuals results of hemoglobin levels in < group> <Exposed Set>

Note: This figure is shown as an example.

**Template 27 Exploratory comparisons between groups in terms of percentage of subjects reported any Grade 2/3 AE and/or any fever >38.5°C and/or any vaccine-related SAE during the 7-day (Days 1-7) post-vaccination period <Exposed Set>**

								Difference in percentage (Group 1 minus Group 2)			
										95 % CI	
Group 1	N	n	%	Group 2	N	n	%	Difference	%	LL	UL
RSV_Ld				Placebo_Ld				RSV_Ld – Placebo_Ld			
RSV_Md				Placebo_Md				RSV_Md – Placebo_Md			
RSV_Hd				Placebo_Hd				RSV_Hd – Placebo_Hd			

**<each group>:**

RSV-Ld = Low dose ChAd155-RSV vaccine (5 x 10^9 vp)

RSV-Md = Middle dose ChAd155-RSV vaccine (1.5 x 10^10 vp)

RSV-Hd = High dose ChAd155-RSV vaccine (5 x 10^10 vp)

Placebo-Ld = Non-active control (0.5 ml)

Placebo-Md = Non-active control (0.15 ml)

Placebo-Hd = Non-active control (0.5 ml)

N = Number of subjects with the administered dose

n/% = number/percentage of subjects reporting a specified symptom

95% CI = Standardized asymptotic 95% confidence interval, LL = Lower Limit, UL = Upper Limit

**Template 28 Percentage of subjects reporting episode of spontaneous or excessive bleeding (AE of specific interest) classified by MedDRA Primary System Organ Class and Preferred Term within the 30-day (Days 1-30) post-vaccination period <Exposed Set>**

Primary System Organ Class (CODE)	Preferred Term (CODE)	Each group N =				
		n*	n	%	LL	UL
At least one symptom						
Gastrointestinal disorders (10017947)	Diarrhoea (10012735)					
	Teething (10043183)					
	Vomiting (10047700)					
General disorders and administration site conditions (10018065)	Pyrexia (10037660)					
Immune system disorders (10021428)	Seasonal allergy (10048908)					
Infections and infestations (10021881)	Conjunctivitis (10010741)					
	Otitis media (10033078)					
	Paronychia (10034016)					
	Tonsillitis (10044008)					
	Tonsillitis streptococcal (10044013)					
	Viral upper respiratory tract infection (10047482)					
Injury, poisoning and procedural complications (10022117)	Arthropod bite (10003399)					
	Face injury (10050392)					
	Head injury (10019196)					
Skin and subcutaneous tissue disorders (10040785)	Miliaria (10027627)					

RSV-Ld = Low dose ChAd155-RSV vaccine (5 x 10^9 vp)

RSV-Md = Middle dose ChAd155-RSV vaccine (1.5 x 10^10 vp)

RSV-Hd = High dose ChAd155-RSV vaccine (5 x 10^10 vp)

Placebo-Ld = Non-active control (0.5 ml)

Placebo-Md = Non-active control (0.15 ml)

Placebo-Hd = Non-active control (0.5 ml)

At least one symptom = at least one symptom experienced (regardless of the MedDRA Preferred Term)

N = number of subjects with at least one administered dose

n\* = number of events reported

n/% = number/percentage of subjects reporting the symptom at least once

95% CI = exact 95% confidence interval; LL = Lower Limit, UL = Upper Limit

**Template 29 Solicited and unsolicited symptoms classified by MedDRA Primary System Organ Class and Preferred Term within the 30-day (Days 1-30) post-vaccination period including number of events - SAE excluded <Exposed Set>**

		<each group> N =		
Primary System Organ Class (CODE)	Preferred Term (CODE)	n*	n	%
At least one symptom				
<each SOC>	<each PT term>			

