#### **6.4.1.2. Between groups assessment**

Exploratory comparisons between the investigational RSV groups and the Placebo groups will be done in terms of the percentage of subjects, overall doses, reporting any Grade 2/3 AE during the 7-day follow-up period (Day 1-7) after vaccination, and/ or any fever  $>38.5^{\circ}\text{C}$  during the 7-day follow-up period (Day 1-7) after vaccination, and/ or any vaccine-related SAE during the 7-day follow-up period (Day 1-7) after vaccination.

The standardized asymptotic 95% CI for the following differences will be computed:

- RSV\_Ld minus Placebo\_Ld
- RSV\_Md minus Placebo\_Md
- RSV\_Hd minus Placebo\_Hd

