**11.3.5. Safety**

- For a given subject and the analysis of solicited symptoms during the 7 day follow-up period after vaccination, missing or non-evaluable measurements will not be replaced. Therefore, the analysis of the solicited symptoms based on the ES will include only vaccinated subjects with documented safety data (*i.e.*, symptom screen completed). More specifically the following rules will be used:
  - Subjects who documented the absence of a solicited symptom after one dose will be considered not having that symptom after that dose.
    - Subjects who documented the presence of a solicited symptom and fully or partially recorded daily measurement over the solicited period will be included in the summaries at that dose and classified according to their maximum observed daily recording over the solicited period.
    - Subjects who documented the presence of a solicited symptom after one dose without having recorded any daily measurement will be considered as having symptom and will be considered in subjects who experiences the symptom but will not be considered in the specific information by grade.
    - Doses without symptom sheets documented will be excluded.
- For analysis of unsolicited AEs, SAEs and for the analysis of concomitant medications, all vaccinated subjects will be considered. Subjects who did not report an event or concomitant medication will be considered as subjects without the event or the concomitant medication respectively.
- Related dose: The related dose for an event (e.g., AE, medication, vaccination...) is the study dose given before an event. In case the event takes place on a day a study dose is given, the related dose will be that of the study dose even if the event actually took place before. For instance, for a conc. medication started on the day of study dose 2 but before dose 2 administrations, the related dose will be dose 2.
- The maximum intensity of local injection site redness and swelling will be scored at GSK Biologicals as follows:
  - 0 : None
  - 1 : < 5 mm
  - 2 : 5 to 20 mm
  - 3 : > 20 mm
- Fever is defined as temperature  $\geq 37.5^{\circ}\text{C}$  /  $99.5^{\circ}\text{F}$  for oral, axillary or tympanic route, or  $\geq 38.0^{\circ}\text{C}$  /  $100.4^{\circ}\text{F}$  for rectal route. The preferred route for recording temperature in this study will be axillary. For the analysis, temperatures will be coded as follows:

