**Template 15 Compliance in completing solicited symptoms information <Exposed Set>**

DOSE	Symptom information	<each group>			<each group>		
		N	n	Compliance (%)	N	n	Compliance (%)
DOSE <each dose number>	General SS						
	Local SS						
TOTAL	General SS						
	Local SS						

RSV-Ld = Low dose ChAd155-RSV vaccine (5 x 10^9 vp)  
 RSV-Md = Middle dose ChAd155-RSV vaccine (1.5 x 10^10 vp)  
 RSV-Hd = High dose ChAd155-RSV vaccine (5 x 10^10 vp)  
 Placebo-Ld = Non-active control (0.5 ml)  
 Placebo-Md = Non-active control (0.15 ml)  
 Placebo-Hd = Non-active control (0.5 ml)  
 N=Number of administered doses  
 n = number of doses with SS returned  
 General SS = Symptom screens used for the collection of general solicited AEs  
 Local SS = Symptom screens used for the collection of local solicited AEs  
 Compliance (%) = (n / N) X 100

**Template 16 Incidence and nature of symptoms (solicited and unsolicited) reported during the 7-day post-vaccination period (Days 1-7) following each dose and overall <Exposed Set>**

		<Each group>					<Each group>					Local symptoms				
					95% CI					95% CI					95% CI	
Dose	Symptoms	N	n	%	LL	UL	N	n	%	LL	UL	N	n	%	LL	UL
Dose 1	Any symptom															
	General symptoms															
	Local symptoms															
Dose 2	Any symptom															
	General symptoms															
	Local symptoms															
Overall/dose	Any symptom															
	General symptoms															
	Local symptoms															
Overall/subject	Any symptom															
	General symptoms															
	Local symptoms															

RSV-Ld = Low dose ChAd155-RSV vaccine ( $5 \times 10^9$  vp)  
 RSV-Md = Middle dose ChAd155-RSV vaccine ( $1.5 \times 10^{10}$  vp)  
 RSV-Hd = High dose ChAd155-RSV vaccine ( $5 \times 10^{10}$  vp)  
 Placebo-Ld = Non-active control (0.5 ml)  
 Placebo-Md = Non-active control (0.15 ml)  
 Placebo-Hd = Non-active control (0.5 ml)

For each dose:

N = number of subjects with the corresponding documented dose

n/% = number/percentage of subjects presenting at least one type of symptom following the corresponding dose

For overall/dose:

N = number of documented dose

n/% = number/percentage of doses followed by at least one type of symptom

For overall/subject:

N = number of documented dose

n/% = number/percentage of subjects presenting at least one type of symptom

95% CI = exact 95% confidence interval, LL = Lower Limit, UL = Upper Limit

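### Template 27, the only vaccine–placebo safety comparison, uses an all-dosed denominator that counts infants without a symptom screen as free of solicited events

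*SAP*

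**What the plan says.** SAP 6.4.1.2 compares each vaccine group with its own placebo group on the "percentage of subjects, overall doses, reporting any Grade 2/3 AE during the 7-day follow-up period (Day 1-7) after vaccination", combined with fever above 38.5°C and vaccine-related SAEs in the same window. The text gives no denominator.

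The shell for this comparison is Template 27, whose title covers "any Grade 2/3 AE and/or any fever >38.5°C and/or any vaccine-related SAE during the 7-day (Days 1-7) post-vaccination period". Its footnote supplies the denominator, "N = Number of subjects with the administered dose", and the numerator, "n/% = number/percentage of subjects reporting a specified symptom".

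SAP 11.3.5 states the missing-data rules by type of event:
- For solicited symptoms, "missing or non-evaluable measurements will not be replaced", and so "the analysis of the solicited symptoms based on the ES will include only vaccinated subjects with documented safety data". Doses with no symptom sheet are excluded. The N table in that section requires a completed symptom screen for solicited local and general symptoms. Protocol 11.6.2 has the same no-replacement rule.
- For unsolicited AEs and SAEs, every vaccinated infant is counted, and an infant with no report is taken to have had no event.

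Two other shells combine solicited and unsolicited events, and they disagree. Template 16 covers the same seven days and, for each dose, uses "N = number of subjects with the corresponding documented dose". Template 29 covers 30 days and uses the administered dose, as Template 27 does.

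**The concern.** Grade 2/3 solicited reactions and temperature reach the analysis through the symptom screen. If the screen is missing, those components are unknown. Template 27 nevertheless keeps the infant in N, so unknown becomes no event, which is the replacement that SAP 11.3.5 rules out for solicited data. SAP Section 9, which lists changes from the planned analyses, does not mention it.

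Reactogenicity is part of the primary objective, and this is the only planned vaccine–placebo difference for safety (SAP 6.2.1 confines immunogenicity to within-group analysis). Groups are small: about 8 to 16 infants per arm in Steps 1 and 2 and about 16 in Step 3. Equal non-return in both arms is enough to pull the difference towards zero, which is the less cautious direction for a safety comparison. The within-group and between-group tables for the same seven days would also rest on different denominators.

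**Working it through.** The plan states no figure that depends on this denominator, so there is none to reproduce. The check is a comparison of rules, followed by an illustration of size.

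**Rules side by side**

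| Place | Events covered | Denominator |
|---|---|---|
| SAP 11.3.5, solicited | solicited | symptom screen completed |
| SAP 11.3.5, unsolicited AEs and SAEs | unsolicited, SAE | all vaccinated |
| Template 16, per-dose rows | both, 7 days | documented dose |
| Templates 17 and 19, overall/subject rows | solicited, 7 days | at least one documented dose |
| Template 29 | both, 30 days | administered dose |
| Template 27 | both plus related SAE, 7 days | administered dose |

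Template 27 therefore applies the unsolicited rule to an endpoint that also has solicited components. Nothing in the SAP says which rule governs a composite.

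**Effect on the estimate**

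Let n be the dosed infants in an arm, k those with no symptom screen and no other qualifying event, x those with an event, and m = k/n. On documented infants the rate is p = x/(n−k). Under Template 27 it is x/n = (1−m)p. With the same m in both arms, the difference under Template 27 is (1−m)(p₁−p₀). A 25-point difference becomes 25 × 0.95 = 23.75, 25 × 0.90 = 22.5, or 25 × 0.80 = 20.0 points at m = 5%, 10% or 20%.

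**Illustration**

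Event counts and missing screens are assumed, because the documents give neither. The group size of 16 is from SAP Table 1. Intervals are Miettinen–Nurminen score intervals, taken as an assumption to be the standardised asymptotic method six named in SAP 11.2. Events are 6 vaccine versus 2 placebo.

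| Missing screens (vaccine, placebo) | Rates | Difference in points (95% CI) |
|---|---|---|
| Template 27, all dosed | 6/16 vs 2/16 | 25.0 (−5.9 to 52.5) |
| Documented, 1 and 1 | 6/15 vs 2/15 | 26.7 (−5.8 to 54.9) |
| Documented, 2 and 2 | 6/14 vs 2/14 | 28.6 (−5.8 to 57.6) |
| Documented, 3 and 0 | 6/13 vs 2/16 | 33.7 (0.4 to 62.2) |
| Documented, 0 and 3 | 6/16 vs 2/13 | 22.1 (−12.0 to 50.8) |

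Check of the one-per-arm case: m = 1/16, and 26.7 × 15/16 = 25.0.

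With 8 per group and 3 versus 1 events, the all-dosed difference is 25.0 points (−20.1 to 62.2). One missing screen per arm gives 3/7 versus 1/7, or 28.6 points (−21.2 to 67.2), on documented infants.

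The last row of the table shows that the direction is not fixed. When screens are missing mainly in the placebo arm, the all-dosed denominator makes the difference larger, not smaller.

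**The case against.** Several points on the other side are sound.

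- **No stated rule is broken outright.** A reader might infer that Template 27 simply contravenes the SAP. The documents do not support that. The no-replacement rule is written for solicited symptoms, the all-vaccinated rule for unsolicited AEs and SAEs, and neither addresses a composite. Template 29 shows that the sponsor uses the administered dose elsewhere for mixed events. What stands is narrower: for the solicited part, the footnote has the effect that 11.3.5 excludes.
- **The footnote is illustrative.** SAP Section 13 says that template displays and footnotes are examples to be adapted, and that minor changes need no amendment. This makes correction easy. It does not supply a denominator, because 6.4.1.2 gives none.
- **Missing screens may be few.** Protocol Table 5 has solicited AEs recorded at several visits, and Protocol 6.6.16 has staff review the diaries with parents and pursue unreturned cards. The SAP criterion is a completed symptom screen, so it would be too strong to say that solicited data are lost whenever a diary is not returned. Template 15 tabulates compliance by dose and group, so an imbalance would be visible.
- **The comparison carries no decision.** Protocol 11.11 and SAP Section 7 call it exploratory or descriptive, with no multiplicity adjustment. Dose escalation rests on IDMC review and the holding rules.

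A reader might also take the row with three missing screens in the vaccine arm only, where the lower limit moves above zero, as a change of conclusion. No document suggests such an imbalance, and no test is planned.

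**Conclusion.** The point holds in a limited form. For a composite of solicited and unsolicited events, Template 27 treats infants without a symptom screen as free of solicited events, and the SAP does not say which of its two denominator rules should apply.

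With equal missingness the difference is diluted by (1−m): about 1.7 points in the example with 16 per group and one missing screen per arm, and 3.6 points with 8 per group. This assumes that the infants without screens have no other qualifying event. With unequal missingness the error can go either way. The documents give no return rate or event rate, so the real size is unknown and probably small. The claims that the footnote always understates the difference, or that it would reverse a finding, are not supported.

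The change is still worth making before results are seen. Afterwards, the choice of denominator for the only vaccine–placebo safety difference would be post hoc.

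**What to change.** In SAP 6.4.1.2 and the Template 27 footnote, define N as subjects with at least one documented dose (symptom screen completed), as in the overall/subject rows of Templates 17 and 19. This also settles what a single administered dose means for an endpoint taken over both doses. Show the all-dosed denominator as a second row, so that an unsolicited Grade 2/3 AE or related SAE in an infant without a screen is not lost from the table.

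Do not admit undocumented infants only when they have an event, because that selects the denominator on outcome and pushes rates up. For example, take 16 infants, 3 without screens, 6 events in all, one of them an unsolicited Grade 2 AE in an undocumented infant. The documented rate is 5/13 = 38.5% and the all-dosed rate 6/16 = 37.5%, but admitting only the undocumented infant with the event gives 6/14 = 42.9%.

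The cost is one footnote, one sentence, one extra row and a slightly smaller N. The documented-dose status is already needed for Templates 16 to 20. One limit remains: an infant documented after only one of two doses still counts as event-free for the solicited part of the other dose. Template 15 should be read alongside.

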**<each group>:**

RSV-Ld = Low dose ChAd155-RSV vaccine (5 x 10^9 vp)

RSV-Md = Middle dose ChAd155-RSV vaccine (1.5 x 10^10 vp)

RSV-Hd = High dose ChAd155-RSV vaccine (5 x 10^10 vp)

Placebo-Ld = Non-active control (0.5 ml)

Placebo-Md = Non-active control (0.15 ml)

Placebo-Hd = Non-active control (0.5 ml)

At least one symptom = at least one symptom experienced (regardless of the MedDRA Preferred Term)

N = number of subjects with the administered dose

n\* = number of events reported

n/% = number/percentage of subjects reporting the symptom at least once

**Template 30 Number (%) of subjects with serious adverse events from vaccination dose 1 up to Day X/Study end including number of events reported <Exposed Set>**

Type of Event	Primary System Organ Class	Preferred Term (CODE)	<each group> N =		
			n*	n	%
SAE	At least one symptom				
	<each SOC>	<each PT term>			
Related SAE	At least one symptom				
	<each SOC>	<each PT term>			
Fatal SAE	At least one symptom				
	<each SOC>	<each PT term>			
Related fatal SAE	At least one symptom				
	<each SOC>	<each PT term>			

**<each group>:**

- RSV-Ld = Low dose ChAd155-RSV vaccine (5 x 10^9 vp)
- RSV-Md = Middle dose ChAd155-RSV vaccine (1.5 x 10^10 vp)
- RSV-Hd = High dose ChAd155-RSV vaccine (5 x 10^10 vp)
- Placebo-Ld = Non-active control (0.5 ml)
- Placebo-Md = Non-active control (0.15 ml)
- Placebo-Hd = Non-active control (0.5 ml)
- N = number of subjects with the administered dose
- n\* = number of events reported
- n/% = number/percentage of subjects reporting the symptom at least once

**CONFIDENTIAL**

204838 (RSV PED-002)  
Statistical Analysis Plan Final

**Template 31 Listing of unscheduled safety visit from vaccination dose 1 up to Day X/study end <Exposed Set>**

Group	Sub. No.	Gender	Country	Race	Age at visit (Month)	Date of sample	Date of previous safety sample	Timing	Laboratory parameter	Result	Unit	Grade
								<timepoint previous to unsched safety>	Hemoglobin			
									Platelet count			
								UNSCHED SAFETY 1	Hemoglobin			
									Platelet count			

**<each group>:**

RSV-Ld = Low dose ChAd155-RSV vaccine (5 x 10^9 vp)

RSV-Md = Middle dose ChAd155-RSV vaccine (1.5 x 10^10 vp)

RSV-Hd = High dose ChAd155-RSV vaccine (5 x 10^10 vp)

Placebo-Ld = Non-active control (0.5 ml)

Placebo-Md = Non-active control (0.15 ml)

Placebo-Hd = Non-active control (0.5 ml)

Please note the listing will be generated on group blinded at D61 and D366 analysis

**CONFIDENTIAL**

204838 (RSV PED-002)  
Statistical Analysis Plan Final

**Template 32 Listing of SAEs reported from vaccination dose 1 up to Day X visit /study end <Exposed Set>**

Group	Sub. No.	Sex	Country	Race	Age at onset (Month)	Verbatim	Preferred term	Primary System Organ Class	MED type	Dose	Day of onset	Duration	Intensity	Causality	Outcome	Seriousness criteria	Potential AESI (preferred term)

**<each group>:**

RSV-Ld = Low dose ChAd155-RSV vaccine (5 x 10^9 vp)

RSV-Md = Middle dose ChAd155-RSV vaccine (1.5 x 10^10 vp)

RSV-Hd = High dose ChAd155-RSV vaccine (5 x 10^10 vp)

Placebo-Ld = Non-active control (0.5 ml)

Placebo-Md = Non-active control (0.15 ml)

Placebo-Hd = Non-active control (0.5 ml)

Potential AESI: AEs potentially related to spontaneous or excessive bleeding or LRTI will be identified based on the list of preferred terms described in section 11 –Annex

Please note the listing will be generated on group blinded at D61 and D366 analysis

**CONFIDENTIAL**

204838 (RSV PED-002)  
Statistical Analysis Plan Final

**Template 33 Listing of AEs related to LRTI and association to RSV infection from vaccination dose 1 up to Day X visit/study end <Exposed Set>**

Group	Sub. No.	Age at onset (month)	Verbatim	Preferred term	MED type	Previous Dose	Day of onset	Start date	End date	Duration	Intensity	Causality	Outcome	Local RSV test result	Date of sample for local testing	Central test RSV A	Central test RSV B	Date of sample for central testing	AESI

RSV-Ld = Low dose ChAd155-RSV vaccine (5 x 10^9 vp)

RSV-Md = Middle dose ChAd155-RSV vaccine (1.5 x 10^10 vp)

RSV-Hd = High dose ChAd155-RSV vaccine (5 x 10^10 vp)

Placebo-Ld = Non-active control (0.5 ml)

Placebo-Md = Non-active control (0.15 ml)

Placebo-Hd = Non-active control (0.5 ml)

AESI: AEs of Special Interest - LRTI identified by the Investigator

\*AEs related to LRTI will be identified based on the list of preferred terms described in in section 12 –Annex 2

**CONFIDENTIAL**

204838 (RSV PED-002)  
Statistical Analysis Plan Final

**Template 34 Listing of RSV-RTI cases identified according to WHO case definitions and RSV-LRTI reported as AESI from vaccination dose 1 up to Day X visit /study end <Exposed Set>**

Group	Sub. No.	Episode nb	Surveillance type	Start date of episode	End date of episode	SpO2	Respiratory rate	Local RSV test	Date of sample for local testing	Central test RSV A	Central test RSV B	Date of sample for central testing	RSV-RTI	RSV-LRTI	RSV-severe LRTI	RSV-very severe LRTI	All-cause LRTI	AESI	Hospitalization
													Yes/No	Yes/No	Yes/No	Yes/No	Yes/NO	Yes/No	Yes/No

